5.8 Total Amount of Blood

The total amount of blood for each subject will vary depending on the course of their disease, duration on treatment, and local laboratory requirements. At any time during the study, if any laboratory abnormalities are found for a subject, additional blood may be drawn for monitoring.

The maximum amount of blood estimated over any approximate 3 month period is from Day 1 through Week 13 where approximately 89.5 mL may be drawn.

6 DISCONTINUATION

6.1 Discontinuation of Individual Subject(s)

A discontinuation is a subject who enrolled in the study and for whom study treatment is permanently discontinued for any reason.

The subject is free to withdraw from the study treatment and/or study for any reason and at any time without giving reason for doing so and without penalty or prejudice. The Investigator is also free to terminate a subject's involvement in the study at any time if the subject's clinical condition warrants it or for reasons of gross noncompliance.

If a subject is discontinued from the study with an ongoing AE or an unresolved laboratory result that is significantly outside of the reference range, the Investigator will attempt to provide follow-up until the condition stabilizes or no longer is clinically significant.

Discontinuation Criteria from Treatment for Individual Subjects:

- Evidence of symptomatic and radiographic disease progression per Investigator's assessment.
- Subject develops an unacceptable drug-related AE, based on the opinion of the Investigator and in consultation with the Medical Monitor
- Seizure of any grade.
- Subject's disease becomes amenable to local or curative treatments.
- Subject is lost to follow up despite reasonable efforts by the Investigator to locate the subject
- There is a significant protocol violation or non-compliance that occurs with a subject that compromises study objectives or subject safety.
- Female subject becomes pregnant
- Subject's death
- Increased liver function tests per discontinuation criteria in Section 5.1.2.1 Dose Modification Plan for LFT Changes

Discontinuation Criteria from Post-Treatment Follow Up for Individual Subjects:

- Subject withdraws consent for further study participation
- Subject is lost to follow up despite reasonable efforts by the Investigator to locate the subject
- Subject's death

6.2 Discontinuation of the Site

If an Investigator intends to discontinue participation in the study, the Investigator must immediately inform the Sponsor.

6.3 Discontinuation of the Study

The Sponsor may terminate this study prematurely, either in its entirety or at any study site, for reasonable cause provided that written notice is submitted in advance of the intended

termination. Advance notice is not required if the study is stopped due to safety concerns. If the Sponsor terminates the study for safety reasons, the Sponsor will immediately notify the Investigator and subsequently provide written instructions for study termination.

A DSMB will be used to monitor safety during the study. Emerging safety issues may lead to a decision to terminate the study.

7 STATISTICAL METHODOLOGY

The statistical analysis will be coordinated by the responsible biostatistician of APGD-US. A Statistical Analysis Plan (SAP) will be written to provide details of the analysis, along with specifications for tables, listings and figures to be produced. The SAP will be drafted before first subject enrolled and finalized before the database soft lock. Any changes from the analyses planned in SAP will be justified in the clinical study report.

Prior to database lock, a meeting for final review of data and tables, listings and figures will be held to allow a review of the clinical trial data and to verify the data that will be used for analysis set classification. If required, consequences for the statistical analysis will be discussed and documented. A meeting to determine analysis set classifications may also be held prior to database lock.

In general, all data will be summarized with descriptive statistics (number of subjects, mean, standard deviation, minimum, median and maximum) for continuous endpoints, and frequency and percentage for categorical endpoints.

7.1 Sample Size

This sample size was primarily determined to provide sufficient clinical experience to support the design of later-stage clinical development, such as phase 3 studies.

Sample size calculations were performed using EAST 5 software based on the following assumptions:

- 2:1 randomization for enzalutamide vs placebo.
- Median OS for placebo and enzalutamide are 7.0 months and 10.77 months (HR=0.65), respectively.
- A study enrollment period of 18 months and a total study duration of 27 months.

With 109 death events, the study can achieve 80% power to detect a statistically significant difference using 1-sided log-rank test with 10% level of significance. Assuming no loss to follow-up, approximately 144 subjects were originally planned to reach this number of events.

7.2 Analysis Set

Detailed criteria for analysis sets will be laid out in Classification Specifications and the allocation of subjects to analysis sets will be determined prior to database hard-lock.

7.2.1 Full Analysis Set (FAS)

The full analysis set will consist of all randomized subjects. This will be the primary analysis set for efficacy analyses using randomized treatments.

7.2.2 Safety Analysis Set (SAF)

For the statistical summary of the safety data, the SAF will be used. The SAF consists of all subjects who took at least one capsule of study medication, and will be used for safety analyses using the actual treatment received.

7.2.3 Pharmacokinetic Analysis Set (PKAS)

The PKAS is defined as the subset of the SAF population for which at least one quantifiable enzalutamide and N-desmethyl enzalutamide concentration value from the same predose sample is available.

7.2.4 Pharmacodynamic Analysis Set (PDAS)

The pharmacodynamic analysis set (PDAS) will include the subjects from the SAF population for whom sufficient pharmacodynamic measurements (a baseline and at least one post baseline value) were collected. The PDAS will be used for all analyses of pharmacodynamic data.

Any formal definitions for exclusion of subjects from the PDAS will be documented in the Classification Specifications.

7.3 Demographics and Other Baseline Characteristics

Demographics and other baseline characteristics will be summarized by treatment group for the FAS and if different for the SAF. Descriptive statistics will include number of subjects, mean, standard deviation, minimum, median and maximum for continuous endpoints, and frequency and percentage for categorical endpoints.

7.4 Analysis of Efficacy

Efficacy analysis will be conducted on the FAS.

7.4.1 Analysis of Primary Endpoint

7.4.1.1 Primary Analysis

The primary endpoint, OS will be defined as the time from the date of randomization until the documented date of death from any cause. Subjects who are still alive at the time of the data cutoff date will be censored on the last date known to be alive or at the data cutoff date, whichever occurs first. The null hypothesis is that OS distributions of the 2 arms are equivalent. The alternative hypothesis is that OS is prolonged in enzalutamide arm. The null hypothesis will be tested using a stratified one-sided log-rank test at the 0.10 level (stratified by geographic region and ECOG performance status). The hazard ratio of the treatment effect along with two-sided 95% CI will also be calculated using a Cox proportional hazard model.

7.4.1.2 Secondary Analysis

A sensitivity analysis of the primary endpoint will be performed using the unstratified test.

7.4.1.3 Subgroup Analysis

The same analysis of the primary endpoint as described in Section 7.4.1.1 will be conducted using the subgroup of AR+ (defined as $\geq 10\%$ of tumor cells with nuclear expression) patients and other subgroups such as age, gender, geographic region, ECOG status and etiology. Results will be presented as forest plots.

7.4.2 Analysis of Secondary Endpoints

Similar analysis of the primary endpoint as described in Section 7.4.1.1 will also be conducted on the secondary endpoint PFS. Patients who have not progressed or died before the data cutoff date for analysis will be censored at the date of last disease assessment which is the date of last scan. Detailed rules for censoring will be provided in the SAP.

7.4.3 Analysis of Exploratory Endpoints

[REDACTED]

7.5 Analysis of Safety

7.5.1 Adverse Events

Safety will be assessed through descriptive statistics for the frequency of TEAEs by system organ class, preferred term, and the NCI CTCAE grade, the frequency of treatment discontinuations due to AEs, vital signs, ECG and laboratory evaluations.

The severity of all AEs is to be evaluated by the Investigator based on the NCI CTCAE, version 4.03. All AEs will be coded to preferred term and system organ class using MedDRA. The number and percentage of subjects with TEAEs will be presented by MedDRA system organ class and preferred term, relationship to study treatment, and NCI CTCAE grade. TEAE is defined as an AE observed during the treatment-emergent period, which is from the first dose date of study drug to 30 days after the last dose date of study drug or the start of subsequent treatment, whichever is first. A subject reporting the same AE more than once is counted once and at the maximum severity or strongest relationship to study drug treatment, when calculating incidence.

The number and percentage of TEAEs, serious TEAEs, AEs leading to discontinuation and TEAEs related to study drug will be summarized by system organ class, preferred term and treatment group. The number and percentage of TEAEs by severity will also be summarized. All AEs will be listed.

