5.5 Adverse Events and Other Safety Aspects

5.5.1 Definition of Adverse Events (AEs)

AEs will be collected from the time of consent until 30 days after the last dose of study drug or initiation of a new antineoplastic or new investigational agent, whichever comes first. An AE is defined as any untoward medical occurrence in a subject administered a study drug or has undergone study procedures and which does not necessarily have a causal relationship with this treatment. An AE can therefore be any unintended sign (including an abnormal laboratory finding), symptom, or disease temporally associated with the use of a study drug, whether or not related to the study drug.

Some countries may have additional local requirements for events that are required to be reported as AEs or in an expedited manner similar to an SAE. In these cases, it is the

Investigator's responsibility to ensure that these AEs or other reporting requirements are followed and the information is appropriately recorded in the source data accordingly.

Adverse events are events that begin or worsen from the time of informed consent through the 30-day Follow-up Period or initiation of a new antineoplastic or new investigational agent, whichever comes first. Treatment-emergent AEs (TEAEs) are events that begin or worsen from the date of first study drug administration through the 30-day Follow-up Period or initiation of new treatment, whichever comes first.

An abnormality identified during a medical test (e.g., laboratory parameter, vital sign, ECG data, physical exam) should be defined as an AE only if the abnormality meets one of the following criteria:

- Induces clinical signs or symptoms
- Requires active intervention
- Requires interruption or discontinuation of study medication
- The abnormality or investigational value is clinically significant in the opinion of the Investigator.

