5.5.7 Monitoring of Common Serious Adverse Events

Common SAEs are SAEs commonly anticipated to occur in the study population independent of drug exposure. SAEs classified as "common" are provided in Appendix 12.2 Common Serious Adverse Events. The list does NOT change the Investigator's reporting obligations or prevent the need to report an AE meeting the definition of an SAE as detailed above. The purpose of this list is to alert the Investigator that some events reported as SAEs may not require expedited reporting to the regulatory authorities based on the classification of "common SAEs" as specified in Appendix 12.2 Common Serious Adverse Events. The Sponsor will monitor these events throughout the course of the study for any change in frequency. Any changes to this list will be communicated to the participating investigational sites. Investigators must report individual occurrences of these events as stated in Section 5.5.5 Reporting of Serious Adverse Events.

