12.2 Common Serious Adverse Events

The following is a list of SAEs that the Sponsor considers to be associated with the disease state being studied. **The list does NOT change the Investigator's reporting obligations or prevent the need to report an AE meeting the definition of an SAE as detailed in Section 5.5.2 Definition of Serious Adverse Event (SAE).** The purpose of this list is to alert the Investigator that some events reported as SAEs may not require expedited reporting to the regulatory authorities based on the classification of "common SAEs". The Investigator is required to follow the requirements detailed in Section 5.5.5 Reporting of Serious Adverse Events (SAE).

For IND safety reporting, single occurrences of the following events may be excluded from expedited reporting to the FDA. If aggregate analysis of these events indicates they occur more frequently with study drug, an expedited IND safety report may be submitted to the FDA.

- Weight loss
- Decreased appetite/Anorexia
- Asthenia / Fatigue/general weakness
- Nausea
- Vomiting
- Jaundice
- Abdominal pain
- Ascites
- Cancer pain
- Hepatomegaly
- Metastatic liver cancer
- Metastases to lung
- Metastases to peritoneum
- Metastases to abdominal lymph nodes
- Metastases to bone
- Bone pain

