7.5.1 Adverse Events

The severity of all adverse events is to be evaluated by the Investigator based on the NCI CTCAE, version 4.03. All adverse events will be coded to preferred term and system organ class using Medical Dictionary for Regulatory Activities (MedDRA). The number and percentage of subjects with treatment emergent adverse events will be presented by MedDRA system organ class and preferred term, relationship to study treatment, and NCI CTCAE grade. A subject reporting the same adverse event more than once is counted once and at the maximum severity or strongest relationship to study drug treatment, when calculating incidence.

The coding dictionary for this study will be MedDRA. It will be used to summarize AEs by SOC and PT.

An overview table will include the following details:

- Number of TEAEs,
- Number and percentage of subjects with TEAEs,
- Number of drug related TEAEs,
- Number and percentage of subjects with drug related TEAEs,
- Number of serious TEAEs,
- Number and percentage of subjects with serious TEAEs,
- Number of serious drug related TEAEs,
- Number and percentage of subjects with serious drug related TEAEs,
- Number of TEAEs leading to withdrawal of treatment,
- Number and percentage of subjects with TEAEs leading to withdrawal of treatment,
- Number of drug related TEAEs leading to withdrawal of treatment,

- Number and percentage of subjects with drug related TEAEs leading to withdrawal of treatment,
- Number of TEAEs leading to death,
- Number and percentage of subjects with TEAEs leading to death,
- Number of drug related TEAEs leading to death,
- Number and percentage of subjects with drug related TEAEs leading to death, and
- Number and percentage of subjects with death.

The number and percentage of subjects with TEAEs, as classified by SOC and PT will be summarized. Summaries will be provided for:

- TEAEs
- drug related TEAEs,
- serious TEAEs,
- grade 3 or higher TEAEs.
- drug related serious TEAEs,
- TEAEs leading to withdrawal of treatment,
- drug related TEAEs leading to withdrawal of treatment,

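### Serious, grade 3 or higher and fatal TEAE counts can mix HCC progression with other events, and no subject count without progression is planned

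*Protocol*

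**What the plan says.** - **Definitions.** Protocol 5.5.1: "An AE is defined as any untoward medical occurrence in a subject administered a study drug or has undergone study procedures". Neither 5.5.1 nor the SAE definition in 5.5.2 exempts progression of HCC or death from it.
- **Disease-associated SAEs.** Protocol 5.5.7: "Common SAEs are SAEs commonly anticipated to occur in the study population independent of drug exposure". Appendix 12.2 has 16 entries. Five are metastatic-disease terms: "Metastatic liver cancer", "Metastases to peritoneum", and metastases to lung, abdominal lymph nodes and bone. The list does not "prevent the need to report an AE meeting the definition of an SAE as detailed in Section 5.5.2"; it only affects expedited reporting to the regulator.
- **Protocol tables.** Section 7.5.1: "The number and percentage of TEAEs, serious TEAEs, AEs leading to discontinuation and TEAEs related to study drug will be summarized", split by system organ class (SOC), preferred term (PT) and arm.
- **SAP tables.** The overview in SAP 7.5.1 has subject counts for serious TEAEs, TEAEs causing withdrawal and fatal TEAEs ("Number and percentage of subjects with TEAEs leading to death"), each with a drug-related version. SOC/PT summaries follow for all, serious, grade 3 or higher and withdrawal TEAEs, and a further SOC/PT summary by grade. No count is given with progression terms removed, and no grouping of such terms is defined.
- **Window.** Treatment runs until progression or another stopping criterion. The treatment-emergent period ends 30 days after the last dose or at the start of subsequent treatment, if earlier (Protocol 7.5.1, SAP 7.5).

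**The concern.** Progression and death are already the efficacy events. Where they are also recorded as AEs, a count of subjects with a serious, grade 3 or higher or fatal TEAE is partly a second reading of efficacy. Progression on drug, and death soon after it, fall inside the treatment-emergent window unless new therapy starts first.

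Evaluating safety in advanced HCC is a stated secondary objective (Protocol 2.1.2). A reader comparing arms on these counts cannot tell how many subjects had a serious or fatal event that was not the cancer advancing. A real excess of toxicity could be diluted or hidden, or a difference could appear where toxicity is equal.

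**Working it through.** The documents give no figure on progression recorded as an AE, so there is no plan figure to reproduce. The first step follows from the table layout. The other two are illustrations on stated assumptions.

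**1. Can the existing tables give the missing count?**
Let N be the subjects in an arm with at least one serious TEAE, and P those with at least one progression-type serious TEAE. The subjects with at least one non-progression serious TEAE number N − P if no one had both kinds, and N if everyone in P also had another kind. Any value between is possible. P itself is not tabulated: with several progression terms it lies between the largest single PT count and the sum of the PT counts. PT lines therefore bound the count but do not give it. The same holds for the grade 3 or higher, withdrawal and by-grade tables.

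**2. What mixing can do to the serious row**
Let t be the true non-progression rate and r the rate at which progression is recorded as an SAE. If the two are independent, the observed rate is 1 − (1 − t)(1 − r). All rates below are assumed; none is in the documents.

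| Case | Enzalutamide | Placebo | Reading |
|---|---|---|---|
| Truth: t = 15% vs 5% | 15% | 5% | ratio 3.0 |
| r = 10% in both arms | 1 − 0.85 × 0.90 = 23.5% | 1 − 0.95 × 0.90 = 14.5% | ratio 1.62 |
| r = 40% in both arms | 1 − 0.85 × 0.60 = 49.0% | 1 − 0.95 × 0.60 = 43.0% | ratio 1.14 |
| r = 20% vs 30% | 1 − 0.85 × 0.80 = 32.0% | 1 − 0.95 × 0.70 = 33.5% | excess hidden |
| t = 10% in both, r = 20% vs 30% | 1 − 0.90 × 0.80 = 28% | 1 − 0.90 × 0.70 = 37% | false difference |
| t = 10% in both, r = 30% vs 20% | 37% | 28% | false difference, reversed |

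Dilution needs no efficacy difference: with equal r, the 10-point gap falls to 9 points (r = 10%) or 6 points (r = 40%).

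**3. An upper illustration for the fatal row**
Inputs: planned median OS of 7.0 and 10.77 months (Protocol 7.1), which agree with the stated hazard ratio since 7.0/0.65 = 10.77. Thirty days is 30/30.4375 = 0.9856 month. The monthly hazard is ln 2/median, and the 30-day risk is 1 − exp(−hazard × 0.9856).
- Placebo: 0.6931/7.0 = 0.0990; risk 9.30%.
- Enzalutamide: 0.6931/10.77 = 0.0644; risk 6.15%.
- Gap: 9.30 − 6.15 = 3.15 points with no difference in toxicity.

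This assumes that every death in the 30 days after the last dose is recorded as a fatal AE, that no new therapy starts in that time, and that the planned hazard ratio persists off drug. If only a share q of these deaths is counted, the gap is q × 3.15, so about 1.6 points at q = 0.5. Doubling the hazard just after stopping gives 17.7% and 11.9%, a gap of 5.8 points, but nothing in the documents supports that multiplier.

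**The case against.** A reader might infer that no TEAE table separates progression. The documents do not support that. Metastasis terms have their own PT lines in the serious, grade 3 or higher and withdrawal tables. Fatal TEAEs appear by term in the by-grade table, because grade 5 is death (Protocol 5.5.4). What remains is the missing subject-level count.

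The drug-related rows also filter. Blinded investigators may call an event not related when underlying disease explains it (Protocol 5.5.3). The filter is only partial: a possible relationship also covers events that concurrent disease could explain, and missing causality counts as related (SAP 6.2.1).

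The premise is an inference. Disease progression is not itself an Appendix 12.2 entry, and neither document says whether it is recorded as an AE. The withdrawal row is weaker still. Progression is a stopping criterion separate from unacceptable drug-related AEs (Protocol 6.1), and disposition is shown by primary reason (SAP 7.2.1). Whether a stop for progression is also coded as an AE is not stated.

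A reader might also infer that the rows are biased in enzalutamide's favour by 3 to 6 points. That does not follow. Treatment runs to progression in both arms, so much progression falls inside the window in either arm, and longer treatment lengthens the window. The gap in the working concerns the fatal row only, on assumed reporting and off-drug hazards. Protocol 12.9 also reports no statistically significant advantage on the primary endpoint.

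Finally, the sponsor monitors the Appendix 12.2 events for changes in frequency, the DSMB sees unblinded safety data, and the safety analysis is descriptive. This lowers the stakes but does not supply the count.

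**Conclusion.** The point holds as a gap in reporting, worth a cheap improvement. Progression is not exempt from AE or SAE reporting, and five metastatic-disease terms are expressly kept reportable. The serious, grade 3 or higher and fatal counts can therefore mix progression with other events; the withdrawal count does so only if a stop for progression is also coded as an AE. The planned tables show part of the split but not the number of subjects with a non-progression event.

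Direction and size depend on recording rates that the documents do not give. The ratios of 1.62 to 1.14 rest on assumed rates and independence. The figures of 9.30% and 6.15% are an upper illustration for one row.

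A reader might go further and conclude that the toxicity comparison should rest on rows without progression. The documents do not support that either: such rows would drop any drug-induced worsening of HCC, and the sponsor itself foresees an aggregate look at whether the listed events are more frequent with study drug (Appendix 12.2).

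**What to change.** Keep all current tables. Add to SAP 7.5.1 supplementary rows by arm for serious, grade 3 or higher, withdrawal and fatal TEAEs, counting subjects with at least one event after excluding:
- the five metastatic-disease terms already in Appendix 12.2; and
- any preferred term for HCC or its progression.

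A list fixed before unblinding is no longer possible, because this protocol version already reports the primary result. The five terms can be taken from Appendix 12.2 as it stands; any term chosen after unblinding should be labelled post hoc. If the database is already hard-locked, SAP section 1 requires the change to be justified in the clinical study report. One sentence saying whether a stop for progression is also coded as an AE would settle the withdrawal row.

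Present the new rows beside the all-TEAE rows, not in place of them. Other Appendix 12.2 entries such as jaundice and ascites stay in, so the separation is of progression-type terms only.

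Cost: one term list and four extra summaries from data already collected. Downside: drug-induced worsening of HCC would show only in the all-TEAE tables and in OS and PFS.
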